Significance 1 – Importance and Health Relevance of the Research. PD is a chronic neurodegenerative condition affecting an estimated 40,000 veterans treated within the VHA; it is the most common neurodegenerative disease after Alzheimer's disease.¹⁹ The American Parkinson Disease Association states that nationally nearly 60,000 new cases a year are diagnosed with PD, joining approximately 1,500,000 people and their families in the US that are afflicted with this disease (<http://www.youngparkinsons.org>). About 10-20% of individuals are under age 50 when they develop PD, most are over age 65 at onset (<http://www.youngparkinsons.org>). PD affects not only mobility and gait but is also often associated with cognitive impairment, mood disorders including anxiety and depression, and other "non-motor" effects that often go unrecognized, with adverse consequences. Research has shown that these psychiatric and behavioral disturbances, cognitive symptoms, and other nonmotor difficulties such as pain, gastrointestinal, and lower urinary tract symptoms are as troubling or often more troubling when compared to motor symptoms.^{1, 20}

While evidence-based treatments exist that are well-documented to improve outcomes for veterans with PD, there are substantial gaps in PD care within and outside of VA. In our previous research, for example, a sample of veterans with PD receiving care at three VA Healthcare Systems in the southwestern US were interviewed. Results indicated that veterans with PD reported receiving education and counseling about care issues rated important by a national panel of PD experts only 49% of the time overall, ranging from 34% for counseling on driving safety to 70% for understanding their PD medications (personal communication: [name] and [name]). Of those with a care need in the prior 6 months, 46% reported this need was unmet (personal communication: [name] and [name]). Sizeable room for improvement was identified for these veterans' needs for rehabilitation, mental health care, and home health care. Medical record reviews conducted in VA facilities in two US regions, found low adherence rates for multiple established quality of care indicators for PD,^{15,17} including low rates of assessments of falls (51%; n/N=139/271) and depression (60%; n/N=163/271), and an association of non-white race with lower rates of depression treatment.^{14,15,17}

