Development of guideline adherence measures for those measures not previously operationalized is following a process in which PD indicator or care goal is converted to review criteria, which are then operationalized through specific clinical variables and chart review questions.¹² Each observable measurement is being mapped to an action/activity performed in the intervention. For example, a veteran with PD who has been identified as experiencing symptomatic orthostatic hypotension, then the patient is to be instructed about salt intake and head elevation for this care goal to be categorized as adherent. As another example, if the patient is taking antihypertensive medications and has symptomatic orthostatic hypotension, then this medication should be decreased.

Table 4. Categories and examples of adherence for selected PD care quality process measures or indicators (excluding assessment process measures)	
Categories of 38 PD indicators	PD QUALITY GOAL ADHERENCE EXAMPLES
Communication, Education, & Continuity	
 • Should have a comprehensive care plan agreed between the individual, their family and/or caregivers and specialist and secondary providers.
Reporting	
 • All veterans should be assessed for abuse.
Diagnosing PD	
 • Diagnosis should be reviewed regularly & re-considered if atypical features develop.
Medication use	
 • Outpatient medical record should contain an up-to-date medication list.
Management of motor symptoms	
 • If receiving therapy with a dopaminergic agent, veteran should be assessed for motor complications at least every 6 months.
Management of non-motor complications	
 • If a veteran with PD is diagnosed with dementia, then an assessment of decision-making capacity should be conducted.
Non-pharmacological approaches/therapies	
 • All veterans with PD who have impairment of ADLs or in walking ability should be referred for physical therapy.
Palliative care	
 • Should have in outpatient chart: an advance directive, documentation of discussion about who would be surrogate decision maker or a search for surrogate, or indication that there is no identified surrogate.

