Health services utilization. Physician visits, emergency department visits, hospital admissions, nursing home admissions (distinct from respite care), home care services, and pharmacy data will be obtained from the VISN-22 Data Warehouse, which includes admissions to non-VA hospitals if the VA reimburses those hospitals for the care delivered. We will include home care services to examine whether there are fewer hospitalizations in the intervention group and thus less need for post-acute home care, and we will examine pharmacy costs to assess whether increased provider contact in the intervention arm results in an increase in pharmacy costs.

Intervention Activities' Time: Start Up and Maintenance. Estimates of start up and maintenance costs will be generated in part from intervention activity logs, as recorded at various sampled dates by the nurse care managers in a Nurse Activities Log, and by an Intervention Activities Log Tool. These logs track the frequency and the time required for care management activities performed by the nurse care managers as well as intervention-related activities (preparing intervention materials for veterans) performed by any other staff assistants.

Research Design and Methods 6 - Recruitment and Enrollment/Consent Processes. A list of eligible veterans with at least two ICD-9 diagnostic codes for PD (332.0) in the administrative data will be generated through a query of the Data Warehouse for VISN 22 from October 1, 2010-\ through 12/31/2014 or until full enrollment is achieved.²⁷ An electronic version of that list will be securely transferred from the VA GLA Data Warehouse programmer who generates it to the study RA, who will sort veteran's names by the provider who has seen the patient at those visits. A CHAPS nurse care manager will review, in CPRS, the VHA Data Warehouse query results received from the VHA Data Warehouse programmer. If there are multiple providers for a given veteran, the provider to whom the name will be sorted will be prioritized in the following way: first, a movement disorder neurologist; second, a general neurologist; and third, a primary care physician. Each provider will be asked to vet his/her respective list, removing any veteran's name that is deemed inappropriate to contact about the study, and having the opportunity to add names of potentially eligible subjects to the list

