Health Services Utilization. Physician visits, emergency department visits, hospital admissions, nursing home admissions (distinct from respite care), home care services, and pharmacy data for the period 12 months preceding enrollment and during the 18 months (or 24 months for the first 204 enrollees) of the intervention will be collected from the VISN-22 Data Warehouse. The VISN-22 Data Warehouse contains detailed clinical data about Veterans Administration care (including hospitalizations, clinic visits, prescribed medications and demographics) for 5 hospitals and 28 community-based clinics within the VA Desert Pacific Healthcare Network. The database includes admissions to non-VA hospitals if the VA reimburses those hospitals for the care delivered. CHAPS investigators will prepare a query to the VISN-22 Data Warehouse in Year 4 for these data on study participants.

Missing-data, respondent dropout, interviewer bias.

Missing-data: Data collected from medical record abstraction and administrative records will be complete and will not contain missing data. All survey data is collected by immediate computer entry using a computer software program (Microsoft Infopath or Microsoft Access) that will be programmed to incorporate appropriate skip patterns and flag invalid entries as the RA administers the telephone survey. This computer based data collection will produce a clean dataset with minimal missing data and no out-of-range entries. Periodic data quality checks will be carried out by the data manager to identify systematic patterns of missingness that may occur during data collection.

Respondent dropout: In order to reduce dropout due to the participant being unreachable, we will collect multiple contact phone numbers at enrollment and implement tracking procedures for contact attempts by the study team as outlines in the human subjects section. A toll-free number will be available for participants to reach the research staff and flexible interview times will be offered to participants. If necessary, surveys can be completed over multiple contacts with the participants.

Interviewer bias: Study research assistants that conduct the telephone surveys, and the nurse abstractors who conduct the medical record abstractions will be blinded to the intervention status of participants.

Data Management and Quality Control. Research subject level data will be maintained in 3 separate files:

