6. **Environmental context and organization support:** Health system and community organization characteristics, other VA care management practices, use of information systems; key leadership support, organizational resource commitment
7. **Veterans’ impressions:** Veteran’s assessment, veteran’s care plan, interactions with the nurse, community organizations, VA social services, use/usefulness of MyHealtheVet, etc.

We will employ a formal card sort approach to theme analysis of the interviews with veterans.⁵⁷ We will organize implementation barrier notes and items from meeting minutes into an excel spreadsheet. In both instances, Drs. [name], [name], and [name] will meet together to come to consensus on sorting the text segments into categories/themes.

Specific Aim #2b. Cost Assessment: Using data collected from the Activity logs and itemized start-up costs, we will estimate separately both fixed and variable start-up and implementation costs of the intervention. Total costs for the intervention implementation will be calculated, broken down as technical assistance costs borne by the research team and implementation costs attributable to clinical staff.

Specific Aim #2b. Health Services Utilization: We will aggregate and compare health services utilization costs between the two study arms. The average cost per patient will be generated based on the administrative data and augmented by selective self-reported healthcare use from the telephone survey. We will calculate the costs associated with health services utilization in the 12 months preceding intervention and during the 18 months of the intervention. Utilization will include physician and emergency room visits, hospital admissions, nursing home admissions, home care services, and pharmacy data. We will determine the units of each service utilized per patient and apply standard unit costs from data costs of VA patient care encounters from

the VA Health Economics Resource Center (HERC). More information on the methods used by HERC to calculate average cost data can be found at: http://www.herc.research.va.gov/methods/methods_cost_ac.asp. The total cost of each participant will be examined between intervention and usual care using a two-sample t test and multivariate regression. Because of potential imbalances associated with the high costs of end-of-life care, we will conduct sensitivity analysis excluding participants who died during the study period.

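### The listed outpatient care for the Aim 2b cost total is physician and emergency visits only, so VA therapy, non-physician mental-health care and social work that CHAPS promotes may go uncounted

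*Combined protocol and SAP*

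**What the plan says.** Three places define the utilization that is to be costed.

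- Research Design and Methods 5, under the heading on health services utilization, draws on the VISN-22 Data Warehouse and lists the items as follows: "Physician visits, emergency department visits, hospital admissions, nursing home admissions (distinct from respite care), home care services, and pharmacy data will be obtained".
- Research Design and Methods 6, Health Services Utilization: the same categories, ending "home care services, and pharmacy data for the period 12 months preceding enrollment" and continuing through follow-up. This section describes the warehouse as holding "hospitalizations, clinic visits, prescribed medications and demographics".
- Research Design and Methods 7, Specific Aim #2b: "Utilization will include physician and emergency room visits, hospital admissions, nursing home admissions, home care services, and pharmacy data". Unit costs come from HERC, and the average cost per patient is "augmented by selective self-reported healthcare use from the telephone survey". Each participant's total is then compared between arms by t test and regression.

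On what CHAPS promotes, Table 4 gives as one adherence example: "All veterans with PD who have impairment of ADLs or in walking ability should be referred for physical therapy". Significance 1 reports sizeable room for improvement in veterans' "needs for rehabilitation, mental health care, and home health care". The Overview of Study Design makes proactive referral, within VA and to community resources, a component of the intervention. The Data Management section and the section on limitations both describe the nurse connecting veterans with medical or other providers and with social services.

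**The concern.** Aim 2b is meant to tell VA leadership, from the VA perspective, what CHAPS costs net of any change in other care. Significance 5 names emergency visits and inappropriate hospitalizations as what might fall. Both are on the list. Some of what CHAPS might raise is not: outpatient therapy, mental-health care given by someone other than a physician, and social work. A service that the intervention itself changes but the cost total does not record is a measurement gap that depends on arm, and randomization does not balance it.

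Two uses of the result are exposed. The first is the offset itself and the business case planned for VISN 22 leadership. The second is the rule at the end of the Aim 2b analysis text, under which a formal cost-effectiveness analysis may be done if CHAPS costs are significantly higher and patient outcomes improve significantly. If CHAPS cost is understated, the first half of that condition is harder to meet.

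**Working it through.** The documents give no unit cost, visit rate or cost SD, and no cost figure to reproduce. The check therefore compares the lists with the intervention, and then illustrates the size on stated assumptions.

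**Step 1. Services promoted by CHAPS or cited as unmet need, against the listed categories**

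| Service | In the list? |
|---|---|
| Movement disorder specialist referral (intervention description) | Yes, as a physician visit |
| Primary-care referral after a positive depression screen (Primary Outcome) | Yes, as a physician visit |
| Home health care (Significance 1) | Yes, as home care |
| Medication changes | Yes, as pharmacy |
| Outpatient physical therapy (Table 4); other outpatient rehabilitation (Significance 1) | Not named; therapy at home or during an admission could fall under listed items |
| Mental-health care by a non-physician (Significance 1) | Not named |
| VA social work or social services (Data Management; limitations) | Not named |
| Community (non-VA) services | Outside the VA perspective, so rightly absent |

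The three unnamed rows are the gap.

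**Step 2. Direction**

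Let *d* be the extra unlisted VA encounters per CHAPS patient relative to usual care, *c* the unit cost, and *f* the share already captured under listed items or self-report. The error in the CHAPS minus usual-care cost per patient is

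B = −(1 − f) × d × c.

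B is negative (CHAPS looks too cheap) if d > 0, zero if d = 0, and positive if d < 0.

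**Step 3. Illustration (d, c and f are all assumed)**

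- f = 0, d = 2, c = $100: B = −$200; over the 150 patients planned for the CHAPS arm, −$30,000.
- f = 0, d = 10, c = $300: B = −$3,000; over 150 patients, −$450,000.
- d = 5, c = $200: B = −$1,000, −$750 or −$500 for f = 0, 0.25 or 0.50.
- f = 0, d = −2, c = $100 to $300: B = +$200 to +$600.

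**Step 4. Against sampling error**

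Take 133 per arm (the analytic sample of 266) and an assumed cost SD of $10,000 to $40,000. The standard error of the difference is SD × √(2/133):

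- $10,000 × √(2/133) = $1,226
- $40,000 × √(2/133) = $4,905

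An error of $1,000 is then 1,000/4,905 = 0.20 to 1,000/1,226 = 0.82 standard errors. The extremes are $200 at the larger SD (0.04) and $3,000 at the smaller SD (2.45).

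**The case against.** The strongest reply is that the list is not closed. It says what utilization will include, and the same paragraph adds self-reported use from the telephone survey. The survey is an appendix that is not in the text reviewed, so it may ask about therapy or counselling. This stands to the extent that one cannot say these services add nothing to a participant's cost. It does not settle the matter: the self-report is described as selective and its items are not named, and three matching lists give an analyst no instruction to pull therapy or social-work encounters from the warehouse.

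A reader might also infer that the plan counts the savings and ignores the added spending. The documents do not support that. Section 5 includes pharmacy expressly to see whether more provider contact raises drug costs; added specialist and primary-care visits are physician visits; home care is listed; and CHAPS program costs are estimated separately.

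A reader might infer that respite care is deliberately excluded. The parenthesis in sections 5 and 6 only defines what counts as a nursing home admission, and section 7 does not carry it.

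The evidence that VA-paid use will rise is indirect. Table 4 scores a referral, not attendance, and some referrals go to community agencies. That is fair, and is why the direction below is conditional.

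Lastly, this touches one part of Aim 2b and no Aim 1 inference. That is true, and it limits the weight of the point.

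**Conclusion.** The point holds in a limited form. The stated categories omit VA outpatient therapy, non-physician mental-health care and social work in all three places, although CHAPS is designed to increase referral to services of this kind. If CHAPS raises those VA encounters as intended and the list is followed, the VA-perspective offset is flattered and the significantly-higher-cost condition is harder to meet.

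It would go too far to call this a certain or one-directional bias. The sign depends on a between-arm difference that the documents do not give, and it would reverse if CHAPS reduced such use. The illustrative $200 to $3,000 per patient rests wholly on assumed encounter counts and unit costs, with none of the extra care captured elsewhere. Against the assumed cost variability it runs from negligible to larger than the standard error, so no change of conclusion is shown. What is established is that the rule as written can give a total that is mismeasured differently by arm, and that this is avoidable.

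**What to change.** In the utilization text of sections 5, 6 and 7, replace the physician-visit item with all VA outpatient encounters, physician and non-physician, including rehabilitation, mental health and social work. Keep emergency visits as their own item, counted once. Cost the encounters with the HERC encounter costs already planned, and report physician visits as a sub-line so that the narrower figure remains visible. Exclude CHAPS nurse contacts already in the program cost. Name the self-reported items to be added, and state how overlap with warehouse records is avoided.

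The cost is one sentence in each place and a wider warehouse query; the source is described as holding clinic visits generally. The query may have to be repeated. Section 6 sets it for Year 4, which ended on 9/30/15 in the December 2015 schedule, while the document is dated 12/5/2016, so one cannot assume that it is still to be written. That schedule also shows follow-up collection in the period to April 2017, which a Year 4 extract could not cover in full. The other downside is that the offset may look less favourable.
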